## Observations, Tests, Assessments

## 4.15 Information Subject to Reporting Requirement during Study/Observation Period and Reporting Schedule

Item	Time	At Eligibility Verification	Enrollment Allocation	Baseline	During Study Treatment						Study Treatment Discontinuation or Completion (Day 7)	Outcome Survey
					1	2	3	4	5	6		
Day		0	0	0	1	2	3	4	5	6		
Inclusion/exclusion criteria verification												
Approval from the independent enrollment supervisory board												
Consent acquisition												
Patient characteristics: sex, date of birth or age, name of the diagnosed primary cancer												
Allocation (study drug) number												
Body height and weight 												
Study drug compliance												
Administration of concomitant therapies												
ECOG PS												
QOL assessment												
NRS												
Blood tests: CRP, white blood cell count, hemoglobin, platelet count, blood glucose test date				 a)							 b)	
Occurrence of adverse event					→							
If discontinued: date of and reason for discontinuation												
Outcome survey: date of death or verification of final outcome, reason for ending trial												

a) Data obtained within the two weeks immediately prior to Day 0 may be referenced.

b) Data obtained within one week from Day 7 may be referenced.

#### Information Subject to Reporting Requirement at Enrollment on Day 0 (baseline)

Have at least two individuals check all categories of information in the following enrollment report and promptly enter the information in the EDC according to the operating procedure for EDC inputs prepared by the data center.

- (1) Participant enrollment number
- (2) Name of study site
- (3) Name of investigator
- (4) Date of enrollment
- (5) Date on which the independent enrollment supervisory board issued an approval to administer IC
- (6) Sex
- (7) Date of birth or age
- (8) Name of the diagnosed primary cancer
- (9) Date of primary cancer diagnosis
- (10) Inclusion criteria verification
- (11) In cases where the exclusion criteria verification resulted in the patient as “otherwise deemed by the attending physician as inappropriate for inclusion in the present trial,” document the basis for such a determination.
- (12) Verification of the status of informed consent (IC) acquisition
- (13) Date of IC acquisition
- (14) Allocation (drug) number
- (15) Name of the individual who reports the double-check
- (16) Date of the double-check

#### 4.16 Information on Survey Period

- (1) In the present trial, out of consideration for participants receiving outpatient palliative care while undergoing home care, conduct the eligibility verification, enrollment, allocation, and baseline survey on the same day (Day 0).
- (2) On the day following enrollment and the baseline survey is defined as Day 1 of the study treatment, which continues until Day 7.
- (3) Out of consideration for participants receiving outpatient palliative care while undergoing home care, the study treatment is to conclude on Day 7.
  - 1) If the next visit of an outpatient participant is postponed due to a holiday/weekend, give the participant an envelope containing a QOL questionnaire and an NRS form on Day 0 and ask the participant to fill out the forms on Day 7, place the forms in the envelope, and bring them to the next outpatient visit.
  - 2) If the next visit of an outpatient participant is postponed due to a holiday/weekend, the investigator (attending physician) is to conduct the ECOG PS survey on the outpatient

visit that is closest to Day 7.

- (4) Conduct an outcome survey on death of participants after discontinuation or completion of the study treatment.

#### 4.17 Information on Data to be Reported

##### 4.17.1 Baseline and Day-0 Data to be Reported

- (1) Enrollment number
- (2) Name of study site
- (3) Name of investigator
- (4) Date of report
- (5) Date of assessment
- (6) Body height and weight
- (7) The ECOG PS assessment is to be performed by the investigator (attending physician).
- (8) Concomitant therapies are defined as the therapies administered on Day 0.
- (9) Assess QOL using the Japanese version of EORTC QLQ-C15-PAL by requesting participants to fill out the form.
- (10) EORTC QLQ-C15-PAL was developed for cancer patients receiving palliative care, and published results of a validation of its Japanese version by the principal investigator of the present trial, among others, are available. Registration with EORTC will take place before use.  
Upon collecting a QOL questionnaire that has been filled out by a participant, check for any missing information immediately.
- (11) Ask participants to rate their fatigue on a numeric rating scale (NRS) of 0 to 10.
- (12) The NRS has been included as a fatigue screening tool in the U.S. National Comprehensive Cancer Network (NCCN) Fatigue Practice Guidelines 2013 and used in earlier studies on fatigue.

The “NRS score by NCCN for rating severity of fatigue” is shown below.

NRS Score	Severity of Fatigue
0	No fatigue
1 to 3	Mild fatigue
4 to 6	Moderate fatigue
7 to 10	Severe fatigue
10	The most severe fatigue imaginable

- (13) Do not collect blood samples for a blood test for the sole purpose of collecting data for the present trial.
- (14) Report data from a blood test performed as part of the usual medical care within the two weeks immediately prior to Day 0, along with the date of the test.
- (15) The blood test shall include parameters subject to substantial variations as a result of the study

drug treatment, including C-reactive protein (CRP), white blood cell count, hemoglobin, platelet count, and blood glucose.

#### 4.17.2 Information to be Reported during Trial Period (Days 1 to 7)

- (1) Ask participants receiving outpatient care to record study drug compliance by making entries in a drug compliance diary (Appendix). Participants who are inpatients may make entries in the drug compliance diary personally or have a clinician (physician, nurse, or pharmacist) do so on their behalf.
- (2) With regard to the administration of concomitant therapies, the investigator (attending physician) is to record any drugs prescribed other than the study drug.
- (3) With regard to occurrence of adverse events, see “5. Adverse Events Assessment and Reporting.”
- (4) An interruption of study treatment is defined as a temporary discontinuation (dose interruption) after one or more doses of the study drug followed by resumption of study drug use. The specific period of and the reason for the interruption of study drug treatment shall be provided.

#### 4.17.3 Information to be Reported at Discontinuation of Study Treatment

- (1) Discontinuation of study treatment is defined as no resumption of the study drug on or before Day 7 after one or more doses of the study drug.
- (2) Upon discontinuing the study treatment, conduct the observations and tests required at discontinuation as soon as possible.
- (3) Ask patients to fill out the QOL questionnaire and NRS form.
- (4) If 3 days' worth of data before study treatment discontinuation are available, use such data as the data at study treatment discontinuation.

#### 4.17.4 Information to be Reported at Completion of Study Treatment (Day 7)

- (1) With regard to the administration of concomitant treatments, the investigator (attending physician) is to record any drugs prescribed other than the study drug.
- (2) The investigator (attending physician) shall perform the ECOG PS assessment.
- (3) Ask participants to assess QOL by filling out the Japanese version of the EORTC QLQ-C15-PAL. Upon collecting a QOL questionnaire that has been filled out by a participant, check for any missing information immediately.
- (4) Ask participants to rate the severity of their fatigue on a scale from 0 to 10 on the NRS form for assessing the level of fatigue.
- (5) Perform a blood test, in principle, on Day 7 (acceptable range Days 8 to 14). However, depending on the patient's condition, it is acceptable to report data from a test conducted within one week from Day 7 on a day that is nearest to Day 7. The reported data are to include the date of the blood test, CRP, white blood cell count, hemoglobin, platelet count, and blood glucose.
- (6) For occurrence of adverse events, see “5. Adverse Events Assessment and Reporting.”
- (7) Participants shall record study drug compliance in the drug compliance diary (Appendix) and

submit the diary to the investigator (attending physician) on Day 7. The investigator (attending physician) shall check the drug compliance diary and transcribe the information into the CRF.

4.17.5 Information to be Reported from the Outcome Survey

- (1) Date of confirmation of death outcome or the final outcome
- (2) Outcome
- (3) Cause of death

## 5 Adverse Events Assessment and Reporting

### 5.1 Definition of Adverse Event

In the present trial, all adverse events occurring during the study treatment are subject to evaluation. An adverse event for which a causal relationship to the study treatment cannot be ruled out is defined as an adverse drug reaction (ADR) to the study treatment. Of the ADRs occurring in the steroid group, those described in the package insert of Betamethasone Tablets (Appendix) are defined as known ADRs, and those not described in the package insert or those described but inconsistent in nature or severity are defined as unknown ADRs (unexpected ADRs).

### 5.2 Adverse Events Assessment

In the present trial, adverse events are assessed based on the Common Terminology Criteria for Adverse Events (CTCAE) v4.0, Japanese Clinical Oncology Group (CTCAE v4.0-JCOG).

### 5.3 Information Investigated

5.3.1 In the event the investigator (attending physician) confirms the occurrence of an adverse event, he/she shall investigate the following.

- (1) Name of event (in principle, the name of the diagnosis)
- (2) Date of occurrence
- (3) Seriousness
- (4) Grade (1, mild; 2, moderate; 3, severe or medically significant but not immediately life-threatening; 4, life-threatening; 5, death related to adverse event)
- (5) Disposition of study treatment (continued, interrupted, discontinued)
- (6) Action (action taken [if any action is taken, explain], no action taken)
- (7) Outcome (resolved, resolving, unchanged, worsened, death, unknown [if the investigation ends with the outcome remaining unchanged, worsened, or unknown, provide a reason])
- (8) Date of outcome confirmation
- (9) Causal relationship to the study treatment (related, not related [basis for determining presence/absence of a causal relationship])

### 5.3.2 Definition of Seriousness

A serious adverse event is defined as any untoward medical occurrence associated with the use of the study drug that

- (1) results in death
- (2) is life-threatening
- (3) requires inpatient hospitalization or causes prolongation of existing hospitalization
- (4) results in persistent or significant disability or incapacity
- (5) is a congenital anomaly, or
- (6) other event or reaction deemed a medically significant condition

### 5.3.3 Grade

Determine the grade of an adverse event according to the following criteria based on the most severe condition during the time period the adverse event was observed.

Grade	Condition	Intervention
1	Mild; asymptomatic or presence of a mild symptom(s)	Clinical finding or laboratory test finding only; no treatment required
2	Moderate; requiring minimal/localized/noninvasive treatment	Limitation in age-appropriate instrumental activities of daily living
3	Severe or medically significant but not immediately life-threatening	Requiring inpatient hospitalization or prolongation of existing hospitalization; disability/incapacity; limitation in activities of daily living
4	Life-threatening	Requiring emergency treatment
5	Death related to adverse event	

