(2) The placebo-controlled design was chosen for the following reasons. 1) The study intends to provide patients appropriate palliative care regardless of whether intervention with a steroid is given and to determine the efficacy of the steroid's effect. Thus, to accurately assess the steroid's effect, placebo is needed as a comparator. The appropriate palliative care mentioned above refers to alleviation (or spiritual care in some facilities) of various distressing physical symptoms (e.g., treatment for dyspnea, in the case of lung cancer, or for nausea, vomiting, and constipation/diarrhea, in the case of gastrointestinal cancer) related to certain types of incipient cancer; pain, insomnia, and other physical symptoms associated with many end-stage cancers; and psychological and social issues. 2) Given that a placebo has the potential to provide a certain effect (placebo effect) in terms of alleviating fatigue, a subjective symptom, it is necessary to assess whether treatment with a steroid in the intervention group provides an added effect over and above the placebo effect. 3) We had the following discussion with collaborating physicians involved in palliative care about whether it is ethical to use a placebo control fatigue in PS2/3 terminal-stage patients with advanced cancer-related fatigue. Based on empirical knowledge derived from clinical practice, unlike pain therapy and other treatments that must be rendered promptly, no standard therapeutic intervention has yet been established to improve the quality of life (QOL) of fatigued patients, and the time to commence such a therapy may vary by about a week in normal clinical practice. Unlike therapies to treat pain, nausea, and dyspnea, which must be rendered promptly based on a specified procedure to determine when to commence treatment in clinical practice, a delay of about a week in giving the placebo group treatment with a steroid for fatigue in the present trial is not considered a material deviation from current clinical practice.

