### 5.3.5 Causal Relationship to Study Treatment

The investigator at each study site shall determine whether an event is causally related to the study treatment based on the following criteria and describe the basis for such a determination in the space for comments.

- (1) Not causally related: in cases where no temporal relationship exists between the occurrence of an adverse event and the study treatment or where the occurrence of the event can be explained by a medically appropriate reason other than the study treatment
- (2) Causally related: in cases where the above does not apply

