#### 6.2.2 Safety Endpoint

Adverse events

See “5. Adverse Events Assessment and Reporting.”

[Rationale for the choice of secondary endpoint (efficacy endpoints)]

To assess the study drug’s safety by comparing the occurrences of adverse events between the steroid group and the placebo group.

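### No CTCAE grade or symptom list is taken on Day 0 and no new-or-worsened rule is stated, so for symptoms already present the adverse event form cannot separate worsening from persistence

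*Protocol*

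**What the plan says.** Safety is a secondary objective, to be judged from the severity and frequency of adverse events (0.2, 2). Section 6.2.2 gives the method: "comparing the occurrences of adverse events between the steroid group and the placebo group".

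- **What counts.** Section 5.1: "all adverse events occurring during the study treatment are subject to evaluation". It adds no condition that the event be new, or worse than before the first dose.
- **How it is graded.** Section 5.2: "adverse events are assessed based on the Common Terminology Criteria for Adverse Events (CTCAE) v4.0". Section 5.3.3 assigns the grade "based on the most severe condition during the time period the adverse event was observed".
- **When it is collected.** In the 4.15 schedule the row "Occurrence of adverse event" is marked for the treatment period, with no entry under baseline. Section 4.17.2 likewise places adverse events in Days 1 to 7.
- **What is recorded per event.** Section 5.3.1 has nine items, including "Date of occurrence", grade, outcome and causality. A pre-treatment grade is not among them.
- **What is recorded on Day 0.** Section 4.17.1 lists height and weight, ECOG PS, concomitant therapies, QLQ-C15-PAL, the fatigue NRS and routine blood values. It lists neither CTCAE grades nor existing symptoms, and nor do the enrollment items that follow the 4.15 schedule.
- **The population.** Section 4.1, in describing background palliative care, refers to "pain, insomnia, and other physical symptoms associated with many end-stage cancers".

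**The concern.** In a population with few symptoms, a worst grade on treatment is close to a change from baseline. Here it is not. A patient with grade 2 insomnia on Day 0 and grade 3 on Day 4 may yield one grade 3 record with no trace of the starting grade. The same patient may yield no record at all, if the site reasons that the symptom began before treatment. The text permits either, and a patient whose insomnia stays at grade 2 throughout meets the same ambiguity.

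If persisting symptoms are counted, they add similar numbers to both arms and shrink a real difference. If worsenings are dropped with them, safety information is lost. No later analysis can repair this, because a statistical analysis plan cannot use a baseline grade that was never collected.

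**Working it through.** The protocol states no figure for the safety comparison, so there is none to reproduce. The arm size used below follows from 4.2: 84 / (1 − 0.20) = 105 per arm.

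**1. Can the recorded items separate worsening from persistence?**

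| Item | What it gives | What it does not give |
|---|---|---|
| Date of occurrence (5.3.1) | New versus earlier onset | Earlier and stable versus earlier and worse |
| Causality (5.3.5) | A reasoned judgement per event | A starting grade. An event is unrelated "where the occurrence of the event can be explained by a medically appropriate reason other than the study treatment", and a cancer symptom already present can supply that reason |
| Outcome category, worsened (5.3.4) | Course of a recorded event | A reference to Day 0 |
| Day 0 concomitant therapies (4.17.1) | A hint that a symptom was being treated | Its severity |
| QLQ-C15-PAL, NRS, ECOG PS (Day 0, Day 7) | Change in the domains covered | A CTCAE grade, or a peak between the two assessments |
| Blood values | Change where routine tests exist | Fixed timing: baseline may be up to two weeks old, the end value up to a week after Day 7, and no sample is drawn solely for the trial |

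None of these supplies a pre-treatment CTCAE grade.

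**2. How large could the dilution be?**

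This is an illustration of one reading, in which persisting symptoms are counted, and of one summary, any event yes or no. Let p be the rate of new or worsened events and b the share of patients, equal in both arms and independent of p, with a counted persisting symptom.

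- Observed rate = b + (1 − b)p, so the difference becomes (1 − b)(p₁ − p₀).
- h = 2·arcsin√p₁ − 2·arcsin√p₀ on the observed rates; power = Φ(|h|·√(n/2) − 1.96), with n = 105 and √52.5 = 7.246.

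Assumed p: 30% on steroid, 15% on placebo. The rates and b are not in the protocol.

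| b | Steroid | Placebo | Difference | h | Power |
|---|---|---|---|---|---|
| 0 | 30.0% | 15.0% | 15.0 points | 0.364 | 75% |
| 20% | 44.0% | 32.0% | 12.0 points | 0.248 | 44% |
| 40% | 58.0% | 49.0% | 9.0 points | 0.181 | 26% |
| 50% | 65.0% | 57.5% | 7.5 points | 0.154 | 20% |

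Worked row, b = 20%: 0.2 + 0.8 × 0.30 = 0.44; 0.2 + 0.8 × 0.15 = 0.32; 0.248 × 7.246 = 1.797; Φ(1.797 − 1.96) = Φ(−0.163) = 0.44.

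A second assumed pair, 25% against 10%, behaves in the same way. By the usual normal approximation, power is 82% at b = 0, 45% at b = 20% and 26% at b = 40%.

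**3. Under the null.** If p₁ = p₀, the observed rates are equal for any b, so counting persisting symptoms creates no false difference.

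**4. Is a high background plausible?** Section 5.5.2 reports events in 41/62 = 66.1% and 44/58 = 75.9% in an earlier two-week placebo-controlled trial. That makes a high any-event rate believable. It does not estimate b, because the protocol does not say how those events were counted.

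**The case against.** The strongest reply has five parts.

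- **Severity is recorded on Day 0.** ECOG PS, QLQ-C15-PAL, the fatigue NRS and, where tested, CRP, white cells, hemoglobin, platelets and glucose are taken at baseline and again at the end. A reader might infer that the trial has no baseline severity at all, and that would be wrong. What is missing is the CTCAE grade and the symptom list.
- **Many steroid harms are unlikely to be present at baseline.** Section 5.5.1 names oral candidiasis, subcutaneous hemorrhage, moon face, mood elevation, hyperglycemia and gastrointestinal hemorrhage. Section 3.2 excludes apparent infection, drug-treated peptic ulcer, delirium and drug-treated diabetes (unless well controlled or not expected to worsen). This stands and narrows the point to terms already present on Day 0.
- **A physician may report a worsening as its own event**, with its own date and a causality comment. The text allows this but does not require it, so practice may vary by site.
- **Randomisation and blinding balance persisting symptoms in expectation.** This also stands. A reader might infer that the safety comparison is biased or invalid under either reading. The documents do not support that: counting persisting symptoms dilutes a true difference, and dropping worsenings costs information without necessarily shrinking the relative contrast.
- **The power figures rest on assumed rates and on an any-event comparison that the protocol does not specify.** That is correct. In a table by term, dilution depends only on that term's own baseline prevalence.

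Worst-grade scoring should not be read as the fault either. It is a workable rule once a baseline grade exists.

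**Conclusion.** The point holds in a limited form. Sections 5.1 and 5.3.3 count and grade events without a new-or-worsened condition, and nothing on Day 0 supplies a CTCAE reference. For terms already present, a recorded grade cannot be read as an increase or as persistence, and reporting may differ between sites. Onset dates, causality comments, patient-reported scores and blood values give partial help only.

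The size is uncertain. On the assumed 30% against 15%, and only if persisting symptoms are counted in an any-event comparison, power falls from 75% to between 44% and 20% as b goes from 20% to 50%. No stated target is broken, since the sample size is set on the fatigue score alone. The primary analysis is unaffected. This is a cheap improvement to a secondary safety endpoint.

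**What to change.** - **Section 4.17.1 and the 4.15 schedule:** on Day 0, alongside the ECOG PS, have the physician record the CTCAE grade of each symptom present.
- **Section 5.1:** define a treatment-period adverse event as one that starts after the first dose, or that rises after the first dose by at least one grade from Day 0.
- **Section 5.3.3:** keep the worst-grade rule, read against the Day 0 grade.
- **Section 6.2.2:** compare those events, and their change in grade, between arms.

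The cost is one short case report form page completed by a physician who is already assessing the patient that day, and slightly more data entry. Sample size, treatment and visits do not change.

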### 5.3.4 Outcome

Outcomes are classified into any one of the following six categories: resolved, resolving, unchanged, worsened, death, and unknown.

The day of outcome confirmation, in cases where the adverse event resolved, was resolving, or resulted in death, is considered the day on which the outcome was actually confirmed. In cases where the follow-up ended with the outcome of unresolved or unknown, the day of the last confirmation of outcome by the investigator (attending physician) is considered the day of outcome confirmation, and the reason for ending the follow-up or why the outcome was unknown shall be described in the space for comments.

